12.1.2 Definitions

For definitions used for endpoint evaluation, see *Section 10.2.1* and *Section 10.2.2*.

12.1.3 Statistical Issues

As this study is exploratory, sample size is not based on typical power calculation for confirming an efficacy as this would require either a too long follow-up or an unrealistic number of patients. Statistical hypothesis testing will be used but to be interpreted as exploratory analysis results. No adjustment for multiplicity will be done. All tests will be two-sided and type-1 error level is set to 0.05, i.e. significance level.

Handling of missing data will be described in detail in the SAP.

12.1.4 Summary Statistics

In general, data will be summarized by means of summary statistics. Continuous data will be presented with the number of observations, mean value, standard deviation, minimum, Q1, median, Q3 and maximum value. Categorical data will be presented as counts and percentages. Visit related data will be summarized up until and including the Nephrectomy Visit. Following this visit, visit related data may in addition be summarized, if applicable, based on results being re-allocated defined based on time intervals or as last available observation. Details for this will be specified in the SAP.

All individual patient data will be listed.

12.1.5 Primary Efficacy Analyses

Two primary endpoints are defined, each one in relation to the two primary objectives. As this trial is not powered to detect a statistically significant difference between treatment groups, *Section 12.2*, the statistical analyses described below should be considered exploratory. No adjustments for multiple testing will be done.

All patients will be followed for survival until date of death can be confirmed or up to 5 years after collection of the last patient's 18 months survival data, whichever comes first. Post-study survival data will be collected as described in *Section 11.3*. The primary analysis will be conducted based on the data collected at the entire study end. If the time point for the collection of post-study survival data at the entire study end, before DBL, differs with more than 2 months compared to the last patient's 18 months post randomization time point, then an additional collection of survival data will be conducted and the first follow-up analysis of post-study survival data will be done, as described in *Section 12.5*.

OS

The primary endpoint median OS after randomization in high-risk and intermediate-risk mRCC patients will be calculated and compared overall and by subgroup using the FAS in the following way:

Survival functions will be displayed graphically using Kaplan-Meier plots, and life table statistics will be produced including summaries of number of events and censored observations. Estimates of 25%, 50% (median) and 75% percentiles of time of survival with corresponding 95% confidence intervals will be calculated. Analysis where the survival functions will be compared between Intuvax+sunitinib, vs. sunitinib alone will be conducted using a log-rank test. Time to death in this analysis will be defined as the time from randomization until the event occurs.

In addition the primary efficacy endpoint will be evaluated using the PPS.

18-month survival rate

The primary endpoint 18-month survival rate after randomization in high-risk and intermediate-risk mRCC patients will be calculated and compared overall and by subgroup using life table statistics including summaries of number of events and censored observations and similar survival statistics as described for the analysis of OS above.

NB: Patients alive at the End-of-Study Visit will be followed for survival until date of death can be confirmed or for a maximum of 5 years after collection of the last patient's 18 months survival data, whichever comes first.

Lost to follow-up patients will be handled as censored observations if date of death cannot be found from medical records or databases (including public records).

12.1.6 Secondary Efficacy Analyses

Secondary efficacy endpoints will be presented descriptively by stratum (High-/Intermediate-risk mRCC patients) as stated explicitly for each endpoint below. Further analyses may be defined in the SAP, if appropriate. All secondary endpoints will be evaluated using the FAS. In addition, the PPS will be used.

PFS from start of sunitinib in intermediate and high-risk mRCC patients

The PFS analysis will be based on the subgroup of patients from FAS that actually had been exposed to at least one dose of sunitinib. PFS will be evaluated using similar survival statistics as described for the analysis of the primary endpoint.

Note: For intermediate-risk patients included in the trial according to protocol versions before version Final 4.0, sunitinib treatment did not have to be initiated at a fixed time point. For these patients, the first imaging assessment after nephrectomy will be used as baseline for evaluation of PFS, irrespective of whether or not the imaging assessment coincided with sunitinib treatment start. Further details will be provided in the SAP.

All other secondary endpoints defined as a time-to-event endpoint will be analyzed using the same statistical approach.

Response rate from Sunitinib Start Visit

Evaluation of response rate, based on CT and according to the RECIST 1.1 guideline, from Sunitinib Start Visit will be based on the subpopulation from FAS who have been exposed to at least one dose of sunitinib. Number of patients with CR, PR, PD, and SD after start of sunitinib will be summarized as described in *Section 12.1.4* for categorical data, using the underlying ordinal scale.

ORR including DCR will be summarized descriptively. Waterfall charts will be used to display the response distribution, details for this will be provided in the SAP. Between group comparison of the proportions will be done using Cochran Mantel Haenzel test including stratum on high-risk and intermediate-risk groups as a fixed factor.

Note: For intermediate-risk patients included in the trial according to protocol versions before version Final 4.0, the first imaging assessment after nephrectomy will be used as baseline for evaluation of ORR, irrespective of whether or not the imaging assessment coincided with sunitinib treatment start. Further details will be provided in the SAP.

Number of infiltrating CD8+ T-cells

The patient median number of CD8+ T-cells based on the counts, as evaluated by Micromorph, from the three (3) areas with most abundant positively stained cells, from the two (2) primary tumor biopsies, and from available diagnostic biopsies (either primary tumor or metastasis), and the patient's tumor area expressing CD8 from the two (2) primary tumor biopsies, as evaluated by HistaIm, will be evaluated for the treatment arms per stratum and in total using summary statistics, as described for continuous data in *Section 12.1.4*.

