8 SELECTION OF STUDY POPULATION

8.1 Number of Patients

The estimated number of patients to be randomized in the study is around 90. The patients will be randomized in a 2:1 (vaccination:control) ratio. Stratification will be done at randomization for intermediate- and high-risk patients, *Section 3.2*, and *Section 9.2*.

The choice of sample size is discussed in *Section 12.2*.

The study will be performed at approximately 25 sites in EU and approximately 5 sites in US. Competitive recruitment will apply.

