9 TREATMENT OF PATIENTS

9.1 Investigational Medicinal Products

9.1.1 Treatment Regimens

Patients will be randomized to one (1) of the following two (2) treatment regimens:

- (i) Two (2) doses of Intuvax (10×10^6 DCs) administered intratumorally into the primary tumor 14 ± 3 days apart followed by nephrectomy and sunitinib initiated five (5) to eight (8) weeks after nephrectomy for all patients (administered dose in accordance with the SmPC/USPI)
- (ii) Sunitinib initiated five (5) to eight (8) weeks after nephrectomy for all patients (administered dose in accordance with the SmPC/USPI)

Patients randomized to Intuvax will have their first vaccination within 28 days from Screening Visit.

All patients will have nephrectomy in accordance with local practice.

Patients randomized to sunitinib only will have nephrectomy done within 63 days from Screening.

Patients randomized to Intuvax will have nephrectomy done 3 days or later after the second vaccination and within 63 days from Screening. A patient randomized to Intuvax will have a 14 to 20 day delay of Nephrectomy as compared to if the patient had been randomized to sunitinib only.

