10.2.2 Secondary Efficacy Variables and Assessments

10.2.2.1 Progression Free Survival (PFS) from Start of Sunitinib

PFS from start of sunitinib is defined as time from Sunitinib Start Visit to PD or death following sunitinib initiation from any cause, whichever occurred first. PFS from start of sunitinib will be evaluated per stratum and in total from the two (2) different treatment arms as a secondary efficacy variable.

Note: For intermediate-risk patients included in the trial according to protocol versions before version Final 4.0, sunitinib treatment did not have to be initiated at a fixed time point. For these patients, the first imaging assessment after nephrectomy will be used as baseline for evaluation of PFS, irrespective of whether or not the imaging assessment coincided with sunitinib treatment start. Further details will be provided in the Statistical Analysis Plan (SAP).

10.2.2.2 Objective Response Rate and Duration of Response and Stable Disease from Start of Sunitinib

Evaluation of tumor response is based on centrally assessed CT scans, *Section 10.4.3*, according to the RECIST 1.1 guideline [1].

Definitions - RECIST v1.1

a) Measurable Disease

The presence of at least one (1) measurable lesion. If the measurable disease is restricted to a solitary lesion, its neoplastic nature should be confirmed by cytology/histology. The same measurable and non-measurable lesions will be followed by RECIST v1.1. Disease progression will be determined using RECIST v1.1 criteria.

- Malignant lymph nodes

To be considered pathologically enlarged and measurable, a lymph node must be >15 mm in short axis when assessed by CT scan (CT scan slice thickness

recommended to be no greater than 5 mm). At baseline and in follow-up, only the short axis will be measured and followed.

- **Baseline documentation of “Target” and “Non-Target” lesions**
All measurable lesions up to a maximum of 2 lesions per organ and 5 lesions in total, representative of all involved organs, should be identified as target lesions and recorded and measured at baseline.

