12.2 Determination of Sample Size

This is a proof of concept study and the number of patients chosen is based on practical considerations and not on a formal statistical power calculation. With around 90 patients randomized 2:1 to vaccination and control, it is expected that 18-month survival rate for high-risk and intermediate-risk mRCC patients overall can be adequately estimated for exploratory purposes but not to confirm the findings as statistical significant.

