5 DATA SETS TO BE ANALYSED

The following analysis sets will be used for the statistical analysis and presentation of data:

- **The safety set:** All randomized patients with at least one safety assessment at Screening.
- **The full analysis set (FAS):** All randomized patients being evaluable for any efficacy endpoint
- **The per protocol set (PPS):** All patients randomized to Intuvax who had both doses of Intuvax administered or patient randomized to sunitinib alone, both having the nephrectomy and who continued the trial without any major protocol violations that could interfere with the objectives of this study. The criteria for PPS, regarding which protocol deviations that warrant exclusions will be determined by the following criteria.
 - Violations to inclusion, exclusion and withdrawal criteria
 - Deviations relating to primary and secondary objectives/endpoints
 - Study medication (Intuvax or Sunitinib): That was not stored and/or prepared and/or administered as defined in the protocol
 - Administration of prohibited concomitant medication
 - Availability of required data

The exact criteria that warrant exclusion from PPS will be documented in relation to review of the reported PDs. The patients excluded with reference to the PD leading to exclusion will be listed and signed off in in the *Pre-Analysis Review Form* before DBL.

The FAS is considered as the primary analysis population, and will be used for all primary and secondary efficacy analyses. The primary efficacy analysis will be repeated using the PPS. Any significant discrepancy between the results from the FAS and the PPS will be analysed and discussed.

Secondary efficacy endpoints defined as to be analyzed after start of sunitinib will be based on the subset of subjects in FAS having at least one dose of sunitinib (or as described for PFS, when subjects were included according protocol versions prior to version 4.0).

Baseline and safety will be presented using the safety set.

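### PFS, response and TTP are tested between arms mainly in patients who started sunitinib, with baseline reset after vaccination and nephrectomy, so randomisation does not protect these comparisons

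*Protocol*

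**What the plan says.** **Population.** Protocol 12.1.6: "The PFS analysis will be based on the subgroup of patients from FAS that actually had been exposed to at least one dose of sunitinib". The same section limits the response analysis in the same way and sends the other time-to-event secondary endpoints, which include TTP, through the PFS approach. SAP 5 says that secondary endpoints analysed after the start of sunitinib "will be based on the subset of subjects in FAS having at least one dose of sunitinib", and then refers to an exception described under PFS.

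**Time origin.** Protocol 10.2.2.1: "PFS from start of sunitinib is defined as time from Sunitinib Start Visit to PD or death following sunitinib initiation". Protocol 3.2 and SAP 6.3.1 make the CT at that visit the baseline for PFS, response and TTP.

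**Exception.** For intermediate-risk patients enrolled before protocol version 4.0, SAP 6.3.6 keeps late starters and never-starters in PFS and starts the clock at the visit after nephrectomy. Protocol 10.2.2.1 and 12.1.6 name the first imaging after nephrectomy instead.

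**Tests.** SAP 6.3.6 uses a stratified log-rank test for PFS, the same method for TTP, and a CMH test for ORR and DCR. Protocol 12.1.3: "All tests will be two-sided and type-1 error level is set to 0.05, i.e. significance level". It also calls all testing exploratory, without multiplicity adjustment.

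**Path to sunitinib.** Protocol 9.1.1 says that a patient allocated to Intuvax "will have a 14 to 20 day delay of Nephrectomy as compared to if the patient had been randomized to sunitinib only". A flow-chart footnote (Protocol 7.2.2) makes the start of sunitinib depend on wound healing.

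**The concern.** The randomised difference between the arms is the vaccine, and both doses are given before the PFS clock starts. Reaching sunitinib requires surviving, having surgery and recovering from it. The vaccine arm does this after two intratumoral procedures and a longer wait. Membership of the analysed set is therefore settled after randomisation, by something that treatment and patient condition can both affect.

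A patient who dies or withdraws before sunitinib leaves the comparison instead of counting as a failure. Tumour growth before the Sunitinib Start CT is absorbed into the new baseline. If failure before sunitinib differs by arm, a log-rank or CMH p-value among starters can point in a different direction from the comparison of the arms as randomised.

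The pre-version-4.0 exception does not repair this. Its time origin is still after randomisation, and one test then mixes two origins.

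**Working it through.** **Plan's own figure.** There is none to reproduce for these endpoints. Protocol 12.2 says "the number of patients chosen is based on practical considerations and not on a formal statistical power calculation". Protocol 8.1 gives "The estimated number of patients to be randomized in the study is around 90" and "The patients will be randomized in a 2:1 (vaccination:control) ratio", so 90 × 2/3 = 60 vaccine and 90 × 1/3 = 30 control.

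**Step 1: time before the clock starts** (Protocol 7.2.1.4, 7.2.1.5, Table 2).
- Latest sunitinib start, either arm: 63 + 8 × 7 = 119 days from Screening, or 119/30.44 = 3.9 months. Exclusion criterion 1 sets the life-expectancy threshold at 4 months, about 122 days.
- Earliest in the vaccine arm: day 19 + 5 × 7 = day 54.
- These count from Screening. Randomisation comes later, so the window after randomisation is shorter.

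**Step 2: possible loss before sunitinib.** Loss = 1 − exp(−ln 2 × t/M), where M is the median time to an event that prevents starting. The documents give no M; 6 to 24 months is assumed.

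| | M = 6 | M = 12 | M = 24 |
|---|---|---|---|
| by day 54 | 18.5% | 9.7% | 5.0% |
| by day 119 | 36.3% | 20.2% | 10.7% |

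**Step 3: the delay alone.** The same formula with t = 14 to 20 days and an assumed median OS of 24 to 12 months gives 1.3% to 3.7%. Of 60 vaccine patients that is 0.8 to 2.2 people.

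**Step 4: ORR illustration** (all inputs assumed). Suppose 30% of starters respond in both arms, and 80% of vaccine v 95% of control patients start. Per randomised patient, ORR is 0.30 × 0.80 = 24.0% v 0.30 × 0.95 = 28.5%, a 4.5-point deficit. Among starters the difference is zero. Swapping the start rates reverses the sign.

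**Step 5: PFS illustration** (all inputs assumed). 2,000 simulated trials of 60 v 30; unstratified two-sided log-rank test at 0.05; 18 months of follow-up; median 10 months; sunitinib at day 97 (vaccine) v day 80 (control); no treatment effect after the start; gamma frailty variance 0, 1 or 2. Any event before the start removes the patient from the starters-only analysis.

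| Pre-start hazard, vaccine v control | HR, starters only | HR, all from randomisation |
|---|---|---|
| equal | 0.99, 0.97, 0.93 | 0.99, 0.99, 0.98 |
| doubled | 1.00, 0.85, 0.77 | 1.28, 1.18, 1.14 |

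With equal hazards the starters-only rejection rate stays at about 5%. With the doubled hazard, significant results favouring vaccine are 3.1% to 8.7% among starters v 0.1% to 0.8% from randomisation. Event times are exact here, so scan timing plays no part, and the all-randomised column counts every early event, which the real data could not do for progression.

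**Step 6: population wording side by side.**
- Exposed subset: Protocol 12.1.6 (PFS, response); SAP 5 (endpoints after sunitinib start); SAP 6.3.6 (response categories).
- FAS: Protocol 12.1.6 opening paragraph (all secondary endpoints); SAP 5 (all primary and secondary efficacy analyses); SAP 6.3.6 (PFS); SAP Appendix 1, section 14.2 (PFS quartile and log-rank tables, ORR/DCR and CMH tables).
- No restriction stated: the SAP 6.3.6 ORR/DCR paragraph.

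**The case against.** The endpoint is openly named as running from the start of sunitinib, and it fits the synergy rationale in Protocol 5.2 and 7.3. It is secondary, and all testing is exploratory. That lowers the stakes, but it does not make the comparison a randomised one.

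A reader might infer more than the documents support:

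- *That only starters are analysed.* The pre-version-4.0 exception in SAP 6.3.6 contradicts this for PFS.
- *That early failures disappear from the trial.* Deaths count in OS and 18-month survival, both from randomisation. RECIST change from Screening to post-nephrectomy is summarised separately, one swimmer plot runs from randomisation, and disposition reports exposure and withdrawal reasons (Protocol 12.1.9). None of these puts early failures back into PFS, TTP or ORR. TTF runs from Screening, but its event is second-line therapy after progression.
- *That no all-randomised analysis is planned.* Parts of both documents are redacted and the FAS wording conflicts. The supportable statement is that none appears in the readable text.
- *That the bias favours the vaccine.* The documents give no start or early-event rates by arm. The larger HR gaps above need an assumed doubling of the pre-start hazard, which would itself be a treatment effect.
- *That PFS and ORR are the main supporting results.* No section says so.

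It is also fair that a PFS clock from randomisation has its own flaw. Follow-up scans are scheduled from the Sunitinib Start Visit (Protocol 7.2.1.6), so they fall later from randomisation in the vaccine arm.

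**Conclusion.** The point holds as a limitation of the secondary comparisons. PFS, response and TTP are conditioned on an event after randomisation, with baseline reset there, and the pre-version-4.0 exception adds a second time origin without removing the problem. The p-values from these tests are not randomised comparisons.

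The amount of any bias is unknown. The 14 to 20 day delay alone does little: 0.8 to 2.2 extra early deaths among 60 patients, and simulated HRs of 0.93 to 0.99. A material distortion needs unequal failure before sunitinib. If the vaccine arm's early hazard were doubled, harm from randomisation (HR 1.14 to 1.28) could appear among starters as no effect or benefit (HR 1.00 to 0.77). All of this rests on assumed medians, frailty and start dates, not trial figures. The primary endpoints are unaffected. This is a cheap improvement.

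**What to change.** Keep the stated endpoints and make these changes in the SAP:

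1. **ORR and DCR.** Add a supportive CMH analysis with all randomised patients in the denominator and non-starters as non-responders (for DCR, as not controlled). State how patients whom Protocol 8.5 reclassifies as screening failures after randomisation are handled.
2. **PFS.** Add a supportive stratified log-rank analysis in all randomised patients, from randomisation to the earliest of PD (against the first post-nephrectomy CT) or death from any cause. Count deaths before sunitinib as events. Give a censoring rule for patients with no post-nephrectomy CT and a rule for deaths after withdrawal, because SAP 6.3.6 counts only deaths before the end of the trial in PFS.
3. **Limits.** State beside that result that progression before the post-nephrectomy CT is not captured, and that scans fall about 14 to 20 days later from randomisation in the vaccine arm, which can lengthen its measured PFS.
4. **Reporting.** Tabulate non-starters and reasons by arm and stratum. Label the starters-only p-values as non-randomised.
5. **Wording.** Reconcile FAS with the exposed subset across Protocol 12.1.6, SAP 5, SAP 6.3.6 and the Appendix 1 table titles. Settle whether the pre-version-4.0 baseline is the visit or the first imaging after nephrectomy.

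Cost: a few SAP lines and tables. Survival is already collected after withdrawal (Protocol 8.5), but patients withdrawn before the Sunitinib Start Visit may have no post-nephrectomy CT. The downside is one more PFS result, with a known scan-timing asymmetry.

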12.1.8 Pharmacokinetic Analysis - N/A

12.1.9 Demographic and Other Baseline Characteristics

A patient disposition will be made including number of patients randomized, exposed to trial drug and completing, or withdrawal from trial (including reason for withdrawal). The number of patients in each analysis set will be included. The patient disposition will be made separately by stratum and overall.

Demographic, medical surgical history and other baseline data will be presented using summary statistics based on the safety set overall and split by stratum.

12.1.10 Exposure to Treatment

All details collected in relation to the Intuvax vaccination will be listed and tabulated if applicable. Nephrectomy data will be listed. Exposure data for sunitinib use will be listed per treatment group and stratum.

